## 1. SAP versions, dates and reasons for revision

Version #1: April 22nd, 2024.

## 2. Trial registration number

NCT04950244

## 3. Study title

Diagnostic performances of the pre-hospital high-sensitivity troponin I (hs-cTnI) to rule-out or rule-in patients with chest pain: a prospective and multi-centric cohort study.

## 5. Background and rationale of study

Chest pain (CP) is a difficult symptom to apprehend in the out-of-hospital setting, due to the complexity required to reliably assess patients over the phone. The current standard of care implies dispatching an out-of-hospital vector (HEMS) in the case of CP highly evocative of acute myocardial infarction (AMI). Risk stratification then requires the collection of a detailed medical history, a physical exam, before performing a 12 and 18-lead ECG.

In the absence of ST-segment deviation, single or trending cardiac troponin levels guide decision making. Few prospective trials evaluate the impact of point-of-care (POC) troponin on prehospital triage of CP and two prospective studies evaluating POC troponin as a clinical decision guide are currently underway.

High sensitivity assays improve patient outcomes by providing a better negative predictive value (NPV) and better rule-in for type 1 and 2 MI. High sensitivity cardiac troponin T (hs-cTnT) and I (hs-cTnI) are now routinely available on POC devices. The Atellica VTLI device offers the possibility of analyzing venous whole blood or capillary samples and returning hs-cTnI values comparable to central laboratory testing. The added advantage of hs-cTnI as opposed to hs-cTnT or standard troponin (cTnT) is its better NPV in ruling out coronary causes of CP. This biomarker offers the added advantage of being highly specific to myocardial injury and is correlated to the degree of muscle necrosis.

The hypothesis of the study is that the use of the high-sensitivity troponin I (hs-cTnI) could be of interest to stratify chest pain patients in pre-hospital setting.

[figure not shown]
## 6. Study type

This is a prospective multi-center cohort-based study.

## 7. Objectives and related endpoints (units and calculations used to derive outcomes)

An adjudication committee oversees the validation of the events considered in the following objectives and outcomes.

The primary objective is to determine the thresholds of the pre-hospital capillary and venous hs-cTnI that maximizes the Youden J index. The event to predict is the non ST-elevation acute coronary syndrome at hospital discharge (NSTEMI). The sensitivity is the proportion of patients with an hs-cTnI level higher or equal to the threshold among the patients with the syndrome. The specificity is the proportion of patients with an hs-cTnI level lower than the threshold among the patients without the syndrome. We will also determine the ROC (receiver operating characteristic) curves and the related areas under the curve (AUC) related to the two methods.

**Figure 1.** Decision tree for ruling-out ruling-in the patients with a suspicious myocardial infarction after their emergency admission.

The secondary objectives of the VALIDATE project are to study the discriminative capacities of the pre-hospital hs-cTnI measured by two different testing methods (capillary and venous whole blood), and to select the method with the best performances. For that purpose, we aim:

- To evaluate the most relevant hs-cTnI measurement between the capillary- and the venous-based methods by i) reporting the concordance between the pre-hospital hs-cTnI measured by the capillary and venous methods, and ii) comparing the related AUCs for discriminating patients with NSTEMI.
- To estimate and compare the discriminative performances of the two methods by considering the Major Adverse Cardiac Events (MACE) occurrence at 30 days (ROC curves, AUCs, and Youden J index). Note that a NSTEMI systematically implies an outcome of MACE at 30 days.

Depending on the results at this stage, the rest of the analyses will be performed according to the venous or the capillary method, depending on their discriminative performances. In case of an equivalence, we will choose the capillary method because of its feasibility in a real-life setting. We will further investigate its usefulness to improve the ruling-in and ruling-out process described in Figure 1. More precisely, we aim:

- To propose a pre-hospital predictive tool of the probability of NSTEMI at hospital discharge. The candidate predictors will be the available demographic, clinical data, and pre-hospital hs-cTnI level.
- To estimate its discriminative capacities by estimating the AUC and comparing its value with the one of the in-hospital HEART score estimated at 0h.
- To estimate its ability to rule-out the patients instead of the in-hospital evaluation at 0h for relieving emergency services, i.e., to achieve a negative predictive value equals to 99% (3) for at least 5% of the patients.
- To estimate its ability to rule-in the patients in the cardiology department instead of the in-hospital evaluation at 0h for reducing the time to treatment of the MI, i.e., to achieve a positive predictive value equals to 65.0% (Figure 1) for at least 10% of the patients.
- To evaluate its increase of capacities for discriminating patients with NSTEMI by considering additionally the venous troponin measured in hospital (difference in the AUC).

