## **10. Sample size**

For the primary objective, we expect a sensitivity of 95%. We aim to include 73 patients for a maximum length of the 95% confidence interval equals 10% (+/-5%). Assuming a NSTEMI prevalence of 10%, 730 patients must be analyzed to achieve this precision. By anticipating a 10% rate of non-exploitable data (missing value, lost to follow-up, etc.), 800 inclusions are necessary.

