## **19. Proposition and validation of a predictive tool for pre-hospital rule-out and rule-in**

The cohort will be divided into two parts: two thirds for learning and one third for validation. The description of the two samples will be performed with the same baseline variables listed in the section 16. No p-value will be computed because of the random allocation of the patients. Instead, standardized mean differences will be estimated to evaluate the comparability of the two samples.

From the learning sample, a logistic model will be estimated with LASSO penalization to select the subset of predictors among the following list of candidates: age, gender, body mass index, active smoking, stented heart disease, bypassed heart disease, compatible clinical history, delay after onset of pain lower than 3h; normal ECG evaluated by the HEMS, and the following risk factors: hypertension, diabetes, hypercholesterolemia, family history and hs-cTnI. The outcome will be the diagnosis of NSTEMI. We will perform a 20-fold deviance-based cross-validation to choose the best tuning parameter.

A particular attention will be paid to the interaction between hs-cTnI and the delay after onset of chest pain because the level of troponin may continue to grow up to three hours after the chest pain. This may lead to increase the proportion of false negatives.

From the validation sample, we will estimate its discriminative capacities by the ROC curve and the related AUC. Its goodness-of-fit will be evaluated by a calibration plot of the observed probabilities against the mean predicted probabilities for five subgroups of equal size. The corresponding Hosmer and Lemeshow statistic will be estimated.

Always from the validation sample, we will compute the in-hospital HEART score at 0h, the related ROC curve and AUC, and its difference with the pre-hospital predictive model.

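### The rule-out and rule-in targets (NPV 99%, PPV 65%) are tied to no confidence limit, and the validation third is too small to demonstrate an NPV of 99%

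*SAP*

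**What the plan says.** Section 7 of the SAP gives two utility targets for the predictive tool. For rule-out it is "to achieve a negative predictive value equals to 99% (3) for at least 5% of the patients". For rule-in it is "to achieve a positive predictive value equals to 65.0% (Figure 1) for at least 10% of the patients". Both are framed as replacing the in-hospital evaluation at 0h.

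Section 19 fixes the data: "The cohort will be divided into two parts: two thirds for learning and one third for validation". Section 20 then estimates, in the validation part, the share free of NSTEMI among patients with predicted probability below 0.3, the share with NSTEMI among those above 0.65, and the size of each group. It states no criterion for calling either target met.

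Section 13 plans two-sided 95% intervals by non-parametric bootstrap for the whole SAP. Section 10 sizes the study for the precision of sensitivity only: "Assuming a NSTEMI prevalence of 10%, 730 patients must be analyzed to achieve this precision", and "By anticipating a 10% rate of non-exploitable data (missing value, lost to follow-up, etc.), 800 inclusions are necessary". No precision or error rate is given for the NPV or PPV.

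**The concern.** A target predictive value with a minimum share does not say how much evidence is needed to call it achieved. The minimum share of a one-third validation sample is a handful of patients, and an observed NPV in so few people says little about the true one. Yet a statement that the tool reaches an NPV of 99% is what would support sparing patients the in-hospital evaluation at 0h.

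The interval method adds to this. A bootstrap of a group with no missed events has nothing to vary, so the planned interval could appear to support 99% where the data are compatible with a much lower value.

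**Working it through.** **Inputs.** Analysed N 730 and NSTEMI prevalence 10% (section 10); validation share one third (section 19); NPV 99% in at least 5% and PPV 65% in at least 10% (section 7); two-sided 95% intervals (section 13); cut-offs 0.3 and 0.65 (section 20).

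**1. The plan's own sample size reproduces.** 1.96² × 0.95 × 0.05 / 0.05² = 72.99, so 73 events; 73 / 0.10 = 730. Allowing 10% loss gives 730 / 0.9 = 811.1, or 730 × 1.1 = 803; the plan's 800 is close to both. None of this addresses the NPV or PPV.

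**2. Size of the validation sample.** 730 / 3 ≈ 243, with about 24 NSTEMI at 10%. The range is 240 (800 × 0.9 / 3) to 267 (800 / 3).

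**3. Can it show an NPV of 99%?** With zero missed in n, the exact (Clopper-Pearson) two-sided 95% lower limit is 0.025^(1/n).
- All 243 ruled out with none missed: 0.025^(1/243) = 98.5%. With 267 it is 98.6%.
- Needed for 99%: ln(0.025) / ln(0.99) = 367.04, so 368 patients with none missed.
- A one-sided 95% limit needs 299, still more than 267.
- Wilson, with none missed, is n / (n + 1.96²). It gives 243 / 246.84 = 98.4%, so it does not rescue the claim.

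**4. The 5% minimum.** 0.05 × 243 = 12.15, so 13 patients (12 to 14 over the range above). One miss in 13 gives 12/13 = 92%, so an NPV of 99% requires none missed.
- Lower limit with 0 of 13 missed: 0.025^(1/13) = 75%.
- Chance of zero missed in 13 patients picked with no skill:

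| Prevalence | Formula | Chance |
|---|---|---|
| 5% | 0.95^13 | 51% |
| 10% (plan) | 0.90^13 | 25% |
| 15% | 0.85^13 | 12% |

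At 10% prevalence, 12 patients give 28% and 14 give 23%. The chance falls quickly as the group grows: 0.9^25 = 7% when 10% are selected and 0.9^49 = 0.6% when 20% are.

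**5. The group that section 20 defines.** A no-skill model at 10% prevalence predicts about 0.10 for everyone, so all 243 fall below 0.3. An NPV of 99% then allows at most 2 missed (1% of 243 = 2.43). With about 24 expected, P(X ≤ 2 | 243, 0.10) is about 3 × 10⁻⁹.

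**6. Rule-in.** 0.10 × 243 = 24.3, so 25 patients; 0.65 × 25 = 16.25, so 17 events meet the target. The exact 95% interval for 17/25 is 46% to 85%. A lower limit above 65% needs 22/25. A no-skill group reaches 17/25 with probability about 5 × 10⁻¹².

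**7. The planned bootstrap.** If the ruled-out group holds no missed event and the model is kept fixed, every resample of that group also holds none. The interval is 100% to 100%, against an exact lower limit of 75% for 0 of 13.

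**The case against.** The strongest reply is that these are late secondary aims, worded as estimation, in a cohort sized for sensitivity. No hypothesis or formal declaration of success is attached, and 95% intervals are planned throughout. It would therefore be wrong to say the targets are judged on point estimates alone. This stands as far as it goes. But section 7 does name values to be achieved, no text says how the intervals bear on that, and the planned interval fails in a group without errors.

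Three stronger readings are tempting and are not supported:
- A reader might infer that a worthless tool would pass the planned rule-out analysis one time in four. It would not. The 25% needs a group at the 5% minimum, while section 20 takes everyone below 0.3, where such a tool almost surely fails (step 5). The figure shows how little evidence the stated minimum carries. It is not an error rate of the analysis. That a cut-off of 0.3 does not itself correspond to an NPV of 99% is a further mismatch between sections 7 and 20, which need reconciling.
- A reader might infer that the target penalises a good tool that rules out more patients. With 98 ruled out and a true NPV of 99%, the chance of observing at least 99% is 0.99^98 = 37%. With 100 ruled out one miss is allowed, and it is 0.99^100 + 100 × 0.01 × 0.99^99 = 74%. The low figure comes from whole-number counts.
- A reader might extend the chance argument to rule-in. Step 6 shows that it does not apply there.

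It can also be said that the SAP never demands a lower limit of 99%. That is true, and it is why a descriptive label is an acceptable remedy.

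**Conclusion.** The concern holds in a limited form. No conclusion about the 99% or 65% target is linked to a confidence limit. By the usual standard of an exact 95% lower limit, no result in a validation sample of 240 to 267 can demonstrate an NPV of 99%. At the 5% minimum, a perfect observed result is compatible with a true NPV as low as 75%. For rule-in, a just-met target is compatible with 46% to 85%.

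This assumes 10% prevalence in the validation part, a validation size of one third of 720 to 800, and a model held fixed when the bootstrap is run. Prevalence affects the 25% figure and the expected event count; the exact limits do not depend on it. The bootstrap collapse arises only when the group has no errors, so it matters most for small ruled-out groups. The matter is secondary to the primary objective, but it governs the study's most practical claim.

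**What to change.** In SAP sections 7 and 20:
- Report NPV and PPV with exact (Clopper-Pearson) or Wilson 95% intervals in place of the section 13 bootstrap, and say why.
- Either base any statement that a target is achieved on a lower limit the sponsor fixes before the analysis, or label both analyses descriptive.
- State that the validation sample cannot demonstrate an NPV of 99%.

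Keep the 5% and 10% shares as the sponsor's targets. Raising the minimum share would change the objective and is not needed to cure the problem.

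The cost is SAP wording only, with no new data. The downside is that the claim the study can make about ruling patients out becomes less favourable.

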## **13. Level of statistical significance (p-values, confidence intervals, one- or two-sided)**

Statistical significances will be achieved for p-values lower the 5% by using two-sided alternative hypotheses and two-sided 95% confidence intervals. The 95%CI will be estimated by non-parametric bootstrap.

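### For the added value of in-hospital troponin, the SAP names only an AUC difference; its confidence interval is a valid estimate but a weak basis for deciding whether the marker adds information

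*SAP*

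**What the plan says.** SAP section 7 closes its secondary objectives by asking how far the tool's discrimination improves "by considering additionally the venous troponin measured in hospital (difference in the AUC"). Sections 18 to 20 do not return to it. They specify no pair of models, no sample and no test for this comparison.

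Two general provisions fill part of the gap. Section 13 sets the inference rule, "Statistical significances will be achieved for p-values lower the 5% by using two-sided alternative hypotheses and two-sided 95% confidence intervals", and adds "The 95%CI will be estimated by non-parametric bootstrap". Section 19 splits the cohort, "two thirds for learning and one third for validation", and takes the tool's AUC and its comparison with the HEART score from the validation part. Section 18 reads a test of an AUC difference from its 95% interval, but only for capillary against venous measurement.

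**The concern.** The two models are nested: the tool, and the tool plus one marker. Under a correctly specified model, no gain in AUC and a zero coefficient for the marker are the same null hypothesis. A likelihood-ratio test addresses that null directly. The AUC difference is a rank summary that behaves badly close to the null, so tests built on it are conservative and lose power.

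The tool already has pre-hospital hs-cTnI among its candidate predictors (section 19), so a modest further gain from a second troponin is plausible. That is the range in which the interval is least informative. A non-significant difference could then be taken to mean that the hospital sample adds little, when the comparison had little chance of showing otherwise.

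**Working it through.** **Inputs from the SAP.** Section 10: expected sensitivity 95%, precision of ±5 points, 73 cases, prevalence 10%, 730 patients analysed. Section 13: two-sided 5%, bootstrap intervals. Section 19: two-thirds to one-third split.

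**The plan's own figure.** 1.96² × 0.95 × 0.05 / 0.05² = 72.99, so 73 cases; 73 / 0.10 = 730 patients. This reproduces. It sizes sensitivity only; no power is stated for any AUC difference.

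**Size of the validation third.** 730 / 3 ≈ 243 patients; 73 / 3 ≈ 24 NSTEMI.

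**Assumptions, not in the SAP.** Tool AUC 0.80 to 0.90; true gain 0 to 0.05; normally distributed scores; added marker independent of the tool score within each outcome class; no LASSO step.

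**Simulation.** Models were fitted on two thirds and AUCs compared on the remaining third, with 800 simulated studies per cell. The AUC difference was judged by a DeLong interval and, in selected cells, by the percentile bootstrap. In the 0.80 and 0.90 rows the bootstrap used 150 studies of 300 resamples; the 0.85 bootstrap cells come from a separate run. The likelihood-ratio test was refitted on the same validation patients. Entries are the percentage of studies that show a gain (AUC) or reject (likelihood ratio).

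| Tool AUC | True gain | DeLong | Bootstrap | Likelihood ratio |
|---|---|---|---|---|
| 0.80 | 0 | 2 | 3 | 4 |
| 0.80 | 0.02 | 19 | 27 | 58 |
| 0.80 | 0.03 | 23 | not run | 77 |
| 0.80 | 0.05 | 35 | 41 | 95 |
| 0.85 | 0 | 1 | 1 | 6 |
| 0.85 | 0.02 | 19 | 20 | 71 |
| 0.85 | 0.03 | 29 | not run | 90 |
| 0.85 | 0.05 | 47 | not run | 99 |
| 0.90 | 0 | 0 | 0 | 6 |
| 0.90 | 0.02 | 26 | 37 | 83 |
| 0.90 | 0.03 | 38 | not run | 96 |
| 0.90 | 0.05 | 62 | 73 | 100 |

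The range of about 20 to 38% joins the bootstrap results at a gain of 0.02 (20 to 37%) with the DeLong results at 0.03 (23 to 38%). In the separate run at tool AUC 0.85, the likelihood-ratio test rejected in 69% at a gain of 0.02 and in 4% at no gain. At a gain of 0.045 the bootstrap interval detected it in 51%, against 98% for the likelihood-ratio test.

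**Why the interval is weak here.** At tool AUC 0.85 and gain 0.02, the estimated difference averages 0.018 with a standard deviation of 0.019. The ratio is 0.018 / 0.019 ≈ 0.9, well short of 1.96. The estimate itself is nearly unbiased; it is imprecise.

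**Sensitivity to correlation.** With a within-class correlation of 0.7 between tool score and in-hospital troponin, tool AUC 0.85 and DeLong intervals, power was 19% against 68% at a gain of 0.019, and 42% against 97% at 0.045.

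**If all 730 patients were used.** For tool AUCs of 0.80 to 0.90, DeLong power is 34 to 69% at a gain of 0.02, 61 to 92% at 0.03 and 92 to 100% at 0.05. The likelihood-ratio test has 96 to 100% throughout.

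**The case against.** The best reply is that section 7 names a quantity to estimate, not a test. The objective asks how far discrimination increases, and the AUC difference answers exactly that. A likelihood-ratio test answers whether a coefficient is non-zero, which for troponin is hardly in doubt and says little about clinical worth. This stands, and it is why the AUC difference should remain the reported effect. It does not remove the point: section 13 invites a significance reading of every interval, and no other basis for inference is offered here.

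A reader might infer that the SAP plans to conclude no added value from an interval containing 0, to the advantage of the pre-hospital pathway. It plans no such thing. Its only rule for equivalence concerns capillary against venous measurement.

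Two further limits stand. The validation third is inferred from section 19, because no sample is assigned to this objective. The tool AUC and the gain are assumed.

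**Conclusion.** The point holds as a minor one. Any significance statement on this objective would rest on the interval of a nested AUC difference. In a validation third of about 24 NSTEMI, that interval would miss a true gain of 0.02 to 0.03 in most studies under the assumptions above, where a likelihood-ratio test on the same patients would detect it in 58 to 96%. The added power is not bought with false positives: with no gain the likelihood-ratio test rejects in 4 to 6%.

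It is tempting to go further and say that a real gain will usually look like no gain. The SAP does not support that, since it fixes neither the sample nor the expected gain. At a gain of 0.05 the bootstrap interval in the validation third already detects 41% and 73% (tool AUC 0.80 and 0.90), and all 730 patients would detect it in 92 to 100% by DeLong.

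**What to change.** In sections 7 and 19, specify the following.

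- **Sample and models.** Use the validation sample. The base logistic model contains the tool's linear predictor as fixed in the learning sample; the extended model adds (log) in-hospital venous troponin. Fixing the linear predictor keeps the models nested. Rerunning the LASSO with the new candidate need not.
- **Test.** Likelihood-ratio test of the added term, two-sided 5%.
- **Effect size.** AUC difference with its bootstrap 95% interval.
- **Interpretation.** An interval that includes 0 is not evidence that in-hospital troponin adds nothing.

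The cost is a few sentences and one extra model fit, with no new data. The downside is that a significant likelihood-ratio test shows added information, not that the gain is clinically worthwhile; the AUC difference and its interval must be read beside it.

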## 8. Inclusion criteria

- Age  $\geq$  18 years.
- Chest pain for which a mobile emergency unit (HEMS) is dispatched for pre-hospital assessment.
- Chest pain evocative of AMI; medio- and retro-sternal, constrictive, radiating into the jaw, neck or left arm.
- Non-qualifying ECG or non-ST elevated ECG
- Non-opposition given by the patient after clear and fair information.

## 9. Non-inclusion criteria

- Qualifying ECG with significant ST-segment elevation.
- Diagnosis of acute coronary syndrome has been ruled out by the HEMS physician.
- Patient care within 20 minutes of pain onset.
- Pregnant and/or breastfeeding women, women of childbearing age without contraception.
- Patients under guardianship, curatorship, or subordination.
- Patients benefiting from reinforced protection.

## **10. Sample size**

For the primary objective, we expect a sensitivity of 95%. We aim to include 73 patients for a maximum length of the 95% confidence interval equals 10% (+/-5%). Assuming a NSTEMI prevalence of 10%, 730 patients must be analyzed to achieve this precision. By anticipating a 10% rate of non-exploitable data (missing value, lost to follow-up, etc.), 800 inclusions are necessary.

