## 18. Description of the hs-cTnI discriminative capacities

The primary objective is to determine the pre-hospital capillary hs-cTnI threshold that maximizes the Youden index. The Euclidean distance (also called the upper-left index) will also be estimated. For the corresponding thresholds, the results will be reported on the related ROC curve. The related effectives (true positives and negatives, false positives and negatives) will be reported. The accuracy will also be computed (proportion of true results). On the same figure, the results related to the pre-hospital venous-based hs-cTnI will be reported. The difference between the two curves will be estimated and the corresponding bilateral test to evaluate the significance will be performed from the 95%CI (confidence interval).

The intra-class correlation coefficient (ICC) will additionally provide a single measure of the agreement between the capillary- and venous-based methods. Two scatter plots will be proposed to represent the degree of concordance: a plot with the pre-hospital venous-based hs-cTnI (y-axis) against the capillary-based measurements (x-axis), and a Bland–Altman plot with the difference between the two measurements (y-axis) against the average of the two measurements (x-axis).

The discriminative performance of the pre-hospital hs-cTnI will then be estimated for the MACE at 30 days as outcome. For that purpose, two ROC curves on the same graph will be plotted for the capillary- and venous-based measurements. The related AUCs and differences will be reported.

Depending on the results at this stage, the rest of the analyses will be performed according to the venous or the capillary method. In case of an equivalence, we will choose the capillary method because of its feasibility in a real-life setting.

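### Section 10's 10% interval length is not a maximum, and it assumes a fixed cut-off, whereas the primary analysis picks the Youden cut-off and reports its sensitivity in the same patients without optimism correction

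*SAP*

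**What the plan says.** Section 10 of the SAP gives the planning value: "For the primary objective, we expect a sensitivity of 95" per cent. It then sets the precision: "We aim to include 73 patients for a maximum length of the 95% confidence interval equals 10% (+/-5" points either way. With an NSTEMI prevalence of 10% this becomes 730 patients analysed, and "By anticipating a 10% rate of non-exploitable data (missing value, lost to follow-up, etc.), 800 inclusions are necessary".

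The primary objective in section 7 is to "determine the thresholds of the pre-hospital capillary and venous hs-cTnI that maximizes the Youden J index". Section 18 repeats it for the analysis: "The primary objective is to determine the pre-hospital capillary hs-cTnI threshold that maximizes the Youden index". At the resulting cut-off, "The related effectives (true positives and negatives, false positives and negatives) will be reported", together with the accuracy. No separate sample is named for this step.

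On intervals, section 13 says only: "The 95%CI will be estimated by non-parametric bootstrap". The one internal validation in the plan is in section 19, where two thirds of the cohort serve for learning and one third for validation. It concerns the LASSO predictive tool: "From the validation sample, we will estimate its discriminative capacities by the ROC curve and the related AUC".

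**The concern.** Two things in section 10 do not carry over to the analysis.

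First, calling 10% a maximum promises a bound. The formula behind it gives the length at one value of sensitivity, and the interval lengthens as sensitivity falls below 95%.

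Second, the formula treats the cut-off as fixed in advance. The analysis searches for the cut-off that maximises J and then counts hits and misses in the patients used for the search. Such a search favours cut-offs that happen to lie just below a case value, so the sensitivity in the cohort flatters the cut-off. A bootstrap interval does not remove this. Section 13 also leaves open whether the cut-off is re-selected in each resample, and whether the interval is meant for the sensitivity at the selected cut-off or at the true optimal one. Analysts following the same text could report different intervals.

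At stake is the missed-NSTEMI rate in a study meant to inform rule-out. If the cohort shows 96% and the chosen cut-off truly has 94%, the misses are about 6 in 100 NSTEMI patients rather than 4.

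**Working it through.** **1. The plan's own figures.** Inputs from section 10: sensitivity 0.95, half-width 0.05, prevalence 0.10; two-sided 95% from section 13.

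n = 1.96² × 0.95 × 0.05 / 0.05² = 72.99, so 73. Then 73 / 0.10 = 730. Both reproduce. Taken literally, 800 × 0.90 × 0.10 = 72 cases and a length of 10.07%; the difference is immaterial.

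**2. Is 10% a maximum?** Wald length = 2 × 1.96 × √(p(1−p)/73), with the exact binomial probability of a length above 10%:

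| True sensitivity | Length with p plugged in (points) | Probability that the length exceeds 10 points |
|---|---|---|
| 95% | 10.0 | 0.50 |
| 90% | 13.8 | 0.94 |
| 85% | 16.4 | >0.99 |
| 80% | 18.4 | >0.99 |

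With 70 of 73 cases detected the length is 9.1 points; with 69 of 73 it is 10.4. Nor is 10% the mean length: averaged over binomial sampling at a true 95% that is 9.5 points. It is simply the length if the observed sensitivity is 95%.

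**3. Size of the optimism.** The SAP gives no marker distribution or AUC, so this step rests on assumptions: normal markers in cases and controls, and the cut-off chosen by maximum J. With 73 cases and 657 controls:

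| AUC | Optimal sensitivity | Mean apparent | Mean true at chosen cut-off | Optimism (points) |
|---|---|---|---|---|
| 0.990 | 95.0% | 96.2% | 93.9% | 2.2 |
| 0.970 | 94.5% | 95.7% | 93.2% | 2.5 |
| 0.961 | 89.4% | 91.0% | 88.2% | 2.9 |
| 0.921 | 84.1% | 86.1% | 82.7% | 3.4 |
| 0.856 | 77.3% | 79.6% | 75.7% | 3.9 |

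The direction is the same throughout. Nearly all of it falls on sensitivity, because cases are few. In the first row J is optimistic by 0.917 − 0.893 = 0.024, which leaves about 0.2 points for specificity.

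**4. Coverage of nominal 95% intervals.** Setting: 72 cases, 648 controls, optimal sensitivity 95%, case SD 0.5, 1 or 2 times the control SD (AUC 0.961, 0.990, 0.991), percentile bootstrap. Ranges span the three shapes and two implementations that differ in the candidate cut-offs searched.

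| Interval | Sensitivity at selected cut-off | Sensitivity at optimal cut-off |
|---|---|---|
| Cut-off re-selected | 67–75% | 77–92% |
| Re-selected and shifted by the optimism | 76–84% | 88–97% |

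At optimal sensitivities of 80 to 90% (one implementation), re-selection covers 79–85% (selected) and 89–96% (optimal); after the shift, 88–92% and 95–98%.

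**5. Baseline without selection.** At a fixed cut-off and a true 95%, exact coverage is already only 87% (percentile bootstrap) or 88% (Wald). Part of the shortfall in step 4 is therefore small-sample discreteness.

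**6. Length at the planning value.** With re-selection the mean bootstrap length is 8.7, 7.9 and 7.8 points in the three shapes. Selection does not make the interval longer than 10 points there.

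**The case against.** The strongest reply is that section 10 states its condition before its target, so the disputed word can be read as no longer than 10% if sensitivity is 95%. Longer intervals at lower sensitivity are a feature of every precision calculation. This has some force: the fault is one of wording, and no sample-size figure changes. But even under the stated condition about half of samples exceed 10 points, so the word is still wrong.

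A second reply is that determining the Youden cut-off most naturally means the population optimum, for which a re-selecting bootstrap loses less coverage. That stands as far as it goes, and it is a reason to name the target. It does not help a reader who will apply the published cut-off and expects the published sensitivity.

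Third, the magnitudes depend on assumed shapes, and the scenarios at 95% sensitivity have AUCs of 0.96 to 0.99, which the SAP nowhere assumes. That is correct. The direction is robust, but the coverage figures are illustrative.

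A reader might also infer that the study is too small, that section 10 contains an arithmetic error, or that selection widens the interval beyond 10 points. The documents support none of these. The figures reproduce, the wider intervals come from lower sensitivity, and at 95% the re-selecting interval is shorter than planned. Nor does the point touch the ROC curves or AUCs, which use no chosen cut-off.

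**Conclusion.** The point holds as a mismatch between the basis of the sample size and the primary analysis. From the SAP's figures alone, 10% is the plug-in Wald length at a fixed cut-off with 95% sensitivity, and it cannot be called a maximum. From the SAP's text alone, the cut-off is chosen and described in the same patients with no optimism correction, since the split in section 19 does not reach this analysis.

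The size of the optimism rests on assumed binormal markers: about 2 to 3 points for sensitivities from 95% down to about 85%, and up to 3.9 at 77%. Percentile bootstrap coverage of the sensitivity at the selected cut-off is roughly 67 to 85%, depending on shape and sensitivity; not all of that shortfall is due to selection. It is worth correcting before analysis, but it does not call the number of inclusions into question.

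**What to change.** No patients need to be added.

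1. **Section 10.** Replace the claim of a maximum by: *length of 10% (Wald) if the observed sensitivity is 95% at a fixed cut-off; about 14, 16 and 18 points at 90, 85 and 80%*. Do not call 10% the expected length, because the mean is 9.5 points.
2. **Sections 13 and 18.** State that the Youden cut-off is re-selected in every bootstrap resample, and name whether the interval targets the sensitivity at the selected or at the optimal cut-off.
3. **Section 18.** Label the in-sample sensitivity as apparent and report the optimism-corrected value beside it: apparent sensitivity minus the mean, over resamples, of (sensitivity in the resample − sensitivity of that resample's cut-off in the full cohort). Do the same for specificity and accuracy.
4. **Interval.** Shifting it by the estimated optimism is a reasonable partial repair. Describe it as approximate, because coverage at the selected cut-off stays below nominal (76 to 84% at 95% sensitivity in the settings above). The point correction is also partial: in one implementation at 95%, the corrected values were 0.942, 0.946 and 0.948 against true values of 0.935, 0.939 and 0.942.

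The cost is SAP wording, a few lines of code in a bootstrap already planned, and slightly less favourable reported figures.
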